Planned enrolment	3 municipalities and 9 municipality districts

Sample size estimation

The required sample size calculated before recruitment of participants aimed to detect a difference of 7 h/week for the primary outcome RUD. Based on the literature[4], we assumed that the number of hours of informal care is 46 h/week with a standard deviation (SD) of 20 h/week. With 80% power and a significance level of 5%, the required sample size was estimated to be 260 dyads. To allow for 20% loss to follow-up, a total of 315 dyads, equaling 105 per municipality, must be included.

The post-hoc sample size calculations based on the outcome PADL showed that by treating the study as an individually randomized stepped wedge design[3], with 3 intervention sequences, 5 periods, effect size of 7h/week, outcome variance of 400, significance level of 5% and within-individual correlation of 0.1075 over the 24 month trial would require a total of 240 dyads to be included. To allow for 20% loss to follow-up, the sample size must reach 288 dyads.

Randomization, blinding and unblinding procedures

Block randomization was performed using a computerized random number generator to allocate individual dyads to the three intervention sequences. We will apply stratification to secure that about one third of the dyads in each treatment sequence will be recruited from each municipality. Research assistants, researchers conducting the analyses and other study personal conducting data collection will be blinded to the randomization order, the dyads will be blinded to group allocation until contacted by their coordinator at start of the intervention period. Given the practice change of the intervention, the municipality home care services and coordinators will be informed about allocation sequence when their clusters entered the intervention period.

Analysis Sets

Full Analysis Set (FAS)

The intention-to-treat population includes all randomized dyads who were assigned a coordinator by the municipality. The dyads will be analyzed separately (i.e., PwD and caregiver), dependent on outcome of interest.

This will be the primary analysis set for baseline summary statistics of demographics, primary, secondary and exploratory efficacy analysis as elaborated in section 10.

Municipal coordinator set (MCS)

All coordinators in all municipality districts

Usage overview of analysis sets table

Analyses	FAS	MCS	
Disposition			
Demographics and background	x		
Medical history			

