In cost-effectiveness analysis the effect is measured in health units (or other outcome measures depending on the context). The outcomes are common health measures in natural units, and the results are presented as cost per effect unit/outcome measure. In cost-utility analysis, also called cost per QALY analysis, the effect is measured as quality-adjusted life years (QALYs) on a scale of 0 (death) and 1 (full health). A quality-adjusted life year (QALY) captures both life years gained and improved health as a result of treatment [8, 9].

The economic evaluation will be measured at society level.

Costs and QALYs will be measured for each phase of 6 months

The cost-effective analysis will relate the difference in total mean costs at societal level per 6 months between all intervention -and usual care phases to the difference in RUD, RSS, QoLs, QALYs, NPI, function level such as ADL and IADL

The analysis will use a discounting rate at 3.5%.

Following other costs studies calculating RUD in an advanced economy setting, our analysis will use 35% of the Norwegian average income to value lost leisure time for retired caregiver.

The primary economic evaluation will use the opportunity cost method to assess the costs of informal caregiving. For a sensitivity analysis, the replacement cost will be used.

Unit costs will be based on information from Statistics Norway and information from the primary health care institutions in each municipalities.

Covariates and strata

In the main statistical analyses, the following covariates are used for both caregivers and PwD.

For PwD: Age, sex, marital status, cohabitation status, number of co-caregivers, clinical characteristics of dementia (dementia etiology, neuropsychiatric symptoms, functional level)

For Caregivers: Age, sex, marital status, cohabitation status, numbers of co-caregivers involved in caregiving for the PwD, work status, use of health care services,

Groups, municipalities

Municipalities will be grouped in the main analysis and used as an adjustment variable (fixed effects). This is not the case for district municipalities as we consider that the dyads are similar within municipalities

Subgroups

In subgroup analyses, the following covariates will be used to define relevant subgroups:

- Gender (male, female)
- Work (retired and working caregivers)
- Caregiver relation (spouse, children)
- Residency (living alone, or with caregiver)

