The definition of treatment assignment as specified in section “Analysis sets” will be used in this section, too.

Deviations from the randomized treatment sequence occurred under the first Covid-19 lockdown, see section Modification History, Changes to the study protocol

Treatment duration

Each municipal coordinators are writing logs, and we will collect the data and calculate total hours of care by the coordinator, divided into different categories.

Descriptive statistics for the total hours of care by the coordinators will be presented.

Delivery of the intervention

One coordinator from the municipal per dyad

Efficacy

Primary efficacy analysis

The primary efficacy analysis variable caregiver burden is based on two variables. The first is RUD, divided in three categories: number of hours the last 30 days invested in personal, instrumental and supervisory care. The second is RSS measured as total score but also

specific and clustered items. Lower hours of informal care as well as lower score of RSS, indicates reduction in caregiver burden.

The null hypothesis states that there are no differences in burden and resource utilization between the LIVE intervention and usual care. The primary alternative hypothesis (H1) states that the LIVE intervention will improve caregiver burden and resource utilization compared with usual care. The secondary alternative hypothesis (H2) is that the LIVE intervention will provide more cost-efficient services than usual care.

H0: LIVE treatment = control

H1: LIVE treatment > control

H2: cost efficiency > control

where LIVE treatment denotes the proportion of caregivers experiencing improvement in care burden. The primary hypothesis will be statistically assessed by means of a χ^2 test on the one-sided significance level of 2.5% (corresponding to 5% two-sided).

We will plot the regression line to visualize the parallel effect for both treatment group and control group.

The significance level will be set to 2.5% (one-sided, corresponding to 5% two-sided), the corresponding level of one-sided CI is 97.5% (corresponding to 95% two-sided).

Missing data

We will pre-specify a list of baseline covariates that are likely associated with the missingness and the outcome, and adjust for these covariates in our primary analyses. This covariate-adjusted analysis will be valid under the missing at random (MAR) mechanism.

Sensitivity and robustness tests of regression analyses and economic evaluation

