Due to the complexity of setting up a causal model in a stepped-wedge design trial, we will run several robustness and sensitivity analyses for primary and secondary efficacy analyses.

Subgroup analyses (demographic and clinical) will be performed and compared with the primary efficacy analysis

Robustness checks will also be performed using clustered or single items on measurements such as NPI, RSS, GDS and QoL.

In the economic evaluation, we will set up a simulation model where we can test different cost levels. We will plot the resulting ICERs graphically as a ratio between costs and the effectiveness/utility or as a distribution with uncertainty in cost / effectiveness plane. Four quadrants represent all combinations of possible outcomes. The more effective outcomes are located right on the x-axis, and with the rise of y-axis the cost of the outcome rises. An ICER

that is more costly and more efficient than care as usual is located in the first quadrant; in case of a more costly and less efficient treatment, ICER is in second quadrant.

Secondary efficacy analyses

Other efficacy analyses will be based on the secondary objectives (QoL measurements and NPI) for both PwDs and caregivers. They will be analyzed on the full analyses set (FAS). Higher scores of QoL (for both EQ-5D-5L and QoL Alzheimer's disease scale) indicates low burden for both PwDs and caregivers. Further, high total scores of NPI indicate high burden for both PwDs and caregivers.

Interim analysis

An interim analysis is not planned.

Software

If not stated otherwise, the data will be analyzed using Stata version 17

Abbreviations

CG – Caregiver

FAS – Full Analysis Set

PwD – Person with dementia

RUD – Resource Utilization Dementia

SD – Standard Deviation

SWD – Stepped Wedge Design

QoL – Quality of Life

MI – Multiple Imputation

MAR – Missing at Random

MNAR – Missing not at Random

References

1. Husebo, B.S., et al., *[contact] the clinical pathway for home-dwelling people with dementia and their caregivers: study protocol for a mixed-method, stepped-wedge, randomized controlled trial*. Trials, 2020. **21**(1): p. 510.

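### The only missing-data rule is an untested MAR assumption, and no rule is given for QALYs or costs after death

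*SAP*

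**What the plan says.** The SAP section Missing data has two sentences. The first announces covariates still to be listed: "We will pre-specify a list of baseline covariates that are likely associated with the missingness and the outcome". The second concludes: "This covariate-adjusted analysis will be valid under the missing at random (MAR) mechanism".

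The section on sensitivity and robustness tests promises that "we will run several robustness and sensitivity analyses for primary and secondary efficacy analyses". What it names are subgroup comparisons, clustered or single items, and varied cost levels in the economic model. Multiple imputation and MNAR occur only in the abbreviation list ("MNAR – Missing not at Random"); no analysis uses either.

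Under Economic evaluation, the utility outcome is "quality-adjusted life years (QALYs) on a scale of 0 (death) and 1 (full health", and a QALY is said to reflect life years gained as well as better health. The accounting unit is the six-month phase: "Costs and QALYs will be measured for each phase of 6 months". No sentence says what happens to QALYs or costs in phases after a death, or distinguishes death and admission from withdrawal.

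**The concern.** In this design every dyad starts under usual care and ends under or after the intervention. Loss that accumulates over 24 months therefore leaves more gaps in post-crossover assessments. If dyads who leave differ from what the model predicts for them, and differ more after crossover than before, the treatment coefficient is biased, and nothing in the plan would show by how much.

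The direction is not known in advance. Loss of heavily burdened caregivers would flatter LIVE. Loss through death or admission, after which informal care hours may fall, could do the opposite.

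For QALYs the issue is definition. A person who has died has no EQ-5D form. If the later phases drop out or are predicted as if the person were alive, a survival difference cannot reach the ICER, which the SAP lists under its primary objective.

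**Working it through.** **Inputs.** From Sample size estimation: difference 7 h/week, SD 20 h/week, 80% power, 5% significance, 260 dyads, 20% loss, 315 dyads, within-individual correlation 0.1075. From Study periods: assessments at months 0, 6, 12, 18 and 24, with the three sequences crossing over after months 0, 6 and 12; 315/3 = 105 dyads per sequence.

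**The plan's own figures.** Per arm, 2 × (1.960 + 0.842)² × 20²/7² = 128.1, rounded up to 129, so 258 in total against the stated 260. Then 260 × 1.2 = 312, close to 315 (nine cells of 35). Only the 20% is carried forward.

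**Where loss falls.** Assumption: loss is even and equal in all sequences, so m = 0, 5, 10, 15, 20% at the five assessments.

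- Usual-care cells (6): (0 + 0 + 0 + 5 + 5 + 10)/6 = 3.3%.
- Post-crossover cells (9): (5 + 2×10 + 3×15 + 3×20)/9 = 14.4%.
- Missing assessments: 105 × 1.50 = 157.5 of 1,575. Post-crossover: 105 × 1.30 = 136.5, or 87%. Of all missing assessments, 20% fall at the end of an active six-month period and 67% in follow-up. The Intervention effect table gives follow-up cells a treatment effect too.
- With constant-hazard loss of 10 to 40% in total, the post-crossover share is 85 to 86%.

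**Effect on the coefficient.** The generalised least squares estimate of beta_1 is a weighted sum of cell means, with weights w from (X′V⁻¹X)⁻¹X′V⁻¹ and V exchangeable at 0.1075. If lost values lie d above their MAR prediction, restoring them moves beta_1 by d × Σ(w × m) over the cells where the departure occurs.

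*Equation (1) as printed (no period term).* Post-crossover weights are 0.0942, 0.1160 and 0.1377 per cell in sequences 1, 2 and 3. Departure after crossover only: 0.0942×0.50 + 0.1160×0.45 + 0.1377×0.35 = 0.147. The usual-care cells with loss have weights −0.1739 (sequence 2, month 6) and −0.1521 (sequence 3, months 6 and 12), adding −0.1739×0.05 − 0.1521×0.15 = −0.0315. Departure in all cells: 0.147 − 0.0315 = 0.116.

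*With period fixed effects.* Weights sum to zero within each month, so a departure common to all cells gives 0. For a departure after crossover only, months 18 and 24 cancel because every sequence has crossed over. The rest is 0.5×0.05 + (0.2182 + 0.2818)×0.10 = 0.075.

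| Departure d after crossover only (assumed) | Shift as printed | Shift with period effects |
|---|---|---|
| 5 h/week | 0.74 | 0.38 |
| 10 h/week | 1.5 (21% of 7) | 0.75 (11% of 7) |
| 20 h/week | 2.9 | 1.5 |

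The multipliers scale with total loss: for 10 to 40% they run from 0.074 to 0.295 as printed and from 0.0375 to 0.15 with period effects.

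**QALYs.** With T the share dead by month 24, evenly accrued and averaged within phases, the mean share dead in the nine post-crossover phases is T × (3 + 2×9 + 3×15 + 3×21)/(9×24) = 0.597T. In the three usual-care phases it is T × (3 + 3 + 9)/(3×24) = 0.208T. Scoring death as 0 rather than missing therefore changes the crude difference by −(0.597 − 0.208) × T × 0.5 years × utility. For T = 5% and utility 0.4 this is −0.004; for T = 20% and utility 0.8 it is −0.031 QALY per phase. Both ranges are assumptions. This shift arises from calendar time alone, with no treatment effect on survival.

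**The case against.** The strongest defence is that equation (1) is a longitudinal mixed model with a participant random effect. Likelihood estimation uses all observed outcomes, so burden that rises and is recorded before a dyad leaves does inform the fit, and the covariates are time-indexed. This stands: MAR here is less fragile than adjustment for baseline covariates suggests, and it is a reasonable primary assumption. It does not extend to the chi-squared test of proportions described under Primary efficacy analysis, and it is no reason to leave the assumption untested.

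The effect is also moderate. At 20% loss, moving beta_1 by the full 7 h/week would need a post-crossover departure of 7/0.1475 = 47 h/week as printed, or 7/0.075 = 93 h/week with period effects. A borderline result is at risk, not a large one.

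Four stronger readings are not supported.

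- A reader might infer that uneven loss biases the comparison by itself. It does not: a departure common to all cells cancels once period effects are in the model. The 0.12d that remains as printed comes from the missing period term, although the Causal model section itself calls time-related confounders important.
- A reader might multiply the month-24 loss of 20% by 10 h/week and call 2 h/week (29% of the target) the bias. That is the worst cell, not the shift in beta_1.
- A reader might infer that the SAP treats deaths as MAR, or contradicts its QALY definition. It does neither. It gives no rule, and the anchor at 0 is equally compatible with scoring 0 after death.
- A reader might infer that all loss goes through the MAR rule. Read literally, the full analysis set keeps only dyads assigned a coordinator, so those lost before their start (about 105 × (5% + 10%) = 16 under even loss) would leave the analysis altogether.

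**Conclusion.** The point holds as an inexpensive improvement. The plan rests on one untested MAR assumption and has no rule for QALYs or costs after death. Other sensitivity analyses are named, but none concerns missing data. With 20% loss accruing evenly and a 10 h/week departure after crossover only, beta_1 shifts by 1.5 h/week as printed or 0.75 with period effects. If lost dyads are worse than predicted, LIVE is flattered by that amount; if they have fewer care hours than predicted, the reverse.

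The timing of loss and the size of d are assumptions; the SAP gives only the 20% total. The QALY gap matters only if the economic evaluation is carried out, which the SAP makes conditional on finding a treatment effect.

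**What to change.** 1. Keep MAR as the primary assumption, list the covariates, and put period fixed effects in equation (1).
2. Add a delta-adjusted multiple-imputation tipping-point analysis for the RUD categories and the RSS total. Vary delta separately for usual-care and post-crossover cells and in both directions, and treat loss by withdrawal separately from loss by death or admission. Express delta in the units analysed; 7 h/week is 30 hours per 30 days.
3. In the cost-utility analysis, set the deceased person's own QALYs and own care costs to 0 from the date of death. Keep a surviving caregiver's utility and costs. Impute only for people who are alive with missing forms.
4. Adjust the intervention-versus-usual-care comparison of costs and QALYs for period. Without this, scoring death as 0 would penalise LIVE through calendar time alone.

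The cost is SAP wording, modest Stata programming, and the need for dates and reasons of loss for each dyad member.

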Efficacy: primary	x		
Efficacy: secondary	x		x
Efficacy: other	x	x	x

General Statistical Methods and Definitions

General statistical methods

The statistical analysis will be presented by treatment group for the different analysis sets as outlined in section 4.

Stepped wedge design (SWD) do not strictly feature a treatment and control group, and thus, the summary statistics will include all participants at baseline, and the characteristics according to intervention sequences.

Continuous variables will be summarized using descriptive statistics (means and interquartile ranges), and categorical variables will be presented by frequencies and percentages. A table will present the number of caregivers and PwD with the following data: missing values, mean, median, standard deviation and confidence intervals.

Means and median as well as percentages will be presented with 1 additional decimal place and standard deviation by 2 additional decimals.

If the number of PwD or caregivers in a category is 0, then percentage will not be displayed.

P-values will be reported to 3 decimal places.

Unless otherwise specified, all statistical tests will be two-sided.

Causal model

Due to the longitudinal structure of the collected trial data, we considered the following linear mixed model to estimate and identify the treatment effect due to the intervention. Our SWD, consisting of $j = 3$ municipalities and 3 steps, is a closed cohort design, and thus, time related confounders are important to adjust for [5] when assessing treatment effect.

Mixed-effects regression is one of the most common approaches when estimating the intervention effect in SWD [6, 7]. In our design, we will consider the following model as our primary analysis model, assuming a constant treatment effect.

$$(1) Y_{ijt} = \beta_0 + O_{ijt}\beta_1 + X_{ijt}\beta_2 + b_i + \epsilon_{ijt}$$

where notation Y_{ijt} refers to the primary outcome caregiver burden (RUD and RSS), elaborated in section 3 Study Design, for individual i nested in municipality j at time point t . O_{ijt} is the treatment indicator (effect of receiving assistance from a municipality coordinator) and β_1 is the average treatment effect parameter of interest. Since the study collects repeated observations from the same participants, we consider a longitudinal regression model that adjusts for participant-level random effect, $b_i \sim N(0, \sigma_b^2)$, which corresponds to a compound symmetric correlation structure.

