$\epsilon_{ijt} \sim N(0, \sigma_\epsilon^2)$ represents random error that changes across t and i .

X_{ijt} constitutes control variables which are demographic, socio-economic and clinical confounders (age, sex, caregiver marital status, work status, ADL function), and stratification variables used in the design stage.

Due to the non-normal distribution of hours and costs we will use both linear mixed-effects, as well as general lineal mixed regression model for assessing both primary variables. For RSS, and other continuous variables, we use Linear Mixed regression model. Log-transformation of the outcome will also be considered to address potential non-normality in the response.

Intervention effect

In secondary analysis, we will further examine the extent to which the treatment effect will depend on the calendar time when COVID lockdown happened, and the potential for delayed effect. We collectively refer these effects as heterogeneous treatment effect, and provide a schematic illustration following Section 3.2 of Li et al. (2020) [6]. The rationale is that there the lockdown during the pandemic may contribute to change in the intervention effect. In addition, the intervention may be most effective when it is first introduced, and the sustained effect may be smaller. Therefore, when modelling the intervention effect, we will allow for heterogeneous effect and assess the robustness of our primary analysis. The table below shows how the intervention effect can differ between periods (t) across different groups (g). The deltas (δ) constitute the intervention effect, and their subscript defines heterogeneous effects where δ_0 is the pre-lockdown intervention effect, δ_0^* is the intervention effect post-lockdown, and δ_1^* is the follow-up post-lockdown treatment effect.

When modelling the intervention effect, we will test the null-hypothesis (H_0)

$$\delta_0 = \delta_0^* = \delta_1^*$$

	$t = 1$	$t = 2$	$t = 3$	$t = 4$
$g = 3$			δ_0^*	δ_1^*
$g = 2$		δ_0^*	δ_1^*	δ_1^*
$g = 1$	δ_0	δ_1^*	δ_1^*	δ_1^*

Economic evaluation

If we identify an average treatment effect on one of the primary and secondary outcomes, we will use cost-efficiency (CEA) and cost-utility analysis (CUA) to evaluate the economic effects of the LIVE treatment.

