- Formal caregiver (whether dyads are receiving care by home nursing)
- Categories of caregiver burden intensity
- Categories of dementia diagnoses

Results from subgroups will be presented for the primary analyses.

Observation and analysis times

Study periods

Timeline															
Groups/participants	Inclusion period	Control group			Kristiansand 3, N=35			Bærum 3, N=35			Bergen 3, N=35				
					Kristiansand 2, N=35										
					Bærum 2, N=35										
					Bergen 2, N=35										
		Kristiansand 1, N=35						Follow up							
Number of months		0	1 2	3 4	5 6	7 8	9 10	11 12	13 14	15 16	17 18	19 20	21 22	23 24	
Date		01.09 2019		01.03 2020		01.09 2020		01.03 2021							

		STUDY PERIOD							
		Enrollment		Allocation	Post-allocation				Close-out
TIMEPOINT	-t	0		t1	t2	t3	t4	t5	
ENROLLMENT:									
Eligibilityscreen	x								
Informed consent	x								
Allocation		x							
INTERVENTIONS:									
1st group			x	x					
2nd group				x	x				
3rd group					x	x			
ASSESSMENTS:									
Baseline variables			x						
Outcome variables				x	x	x	x	x	

The stepped wedge randomized control design. A) The randomization in time takes place at month 0. First group (red) is in the intervention period from month 1 to 6, second group (yellow) from month 7 to 12, third group (green) from month 13 to 18. Implementation seminars will be held at month 0, 6 and 12, midway evaluation at month 3, 9 and 15. Data will be collected at baseline (month 0), after first intervention period (month 6-7), after second intervention period (month 12-13), after third intervention period (month 18-19) and at end of study at 24 months. B) Schedule of enrollment, interventions and assessments over the study period.

Demographics and Background Characteristics

Demographics and baseline characteristics

The following demographic characteristics will be presented descriptively and listed for both PwD and caregiver:

- Sex (male, female)
- Age in years
- Marital status (spouse, child)
- Work status (employed, unemployed, retired)
- Number of co-caregivers
- MMSE total score
- RUD (number of care hours the last 30 days)
- RSS total score
- NPI total score
- QoL total score

Date of informed consent and protocol version will be listed

Medical history

We will provide information on the number of years since formal diagnosis of dementia together with descriptive statistics.

Exposure and Compliance

Treatment groups

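### Subgroup results are set against the overall result as a robustness check, and the SAP contains no test of whether the treatment effect differs between subgroups

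*SAP*

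**What the plan says.** Under Covariates and strata, Subgroups, the SAP states: "In subgroup analyses, the following covariates will be used to define relevant subgroups". Seven factors follow: gender, work, caregiver relation, residency, receipt of home nursing, "Categories of caregiver burden intensity", and dementia diagnosis. The list closes with: "Results from subgroups will be presented for the primary analyses".

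The only statement on how the results will be used is in Sensitivity and robustness tests of regression analyses and economic evaluation. That section opens by announcing that "we will run several robustness and sensitivity analyses for primary and secondary efficacy analyses", and then says: "Subgroup analyses (demographic and clinical) will be performed and compared with the primary efficacy analysis".

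The Causal model section presents equation (1) with the words "we will consider the following model as our primary analysis model, assuming a constant treatment effect". It has one treatment coefficient and no treatment-by-factor term. The one test of heterogeneity, under Intervention effect, asks whether the pre-lockdown, post-lockdown and follow-up effects are equal. It concerns time, not subgroups. The SAP gives no criterion for the subgroup comparison and no rule for interpreting several such comparisons.

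**The concern.** A robustness check keeps the question and the population and varies an assumption. A subgroup analysis changes the population and cuts the sample. Agreement with the overall estimate is partly built in, because the subgroup contributes to it. Disagreement is expected from the smaller sample alone. Neither tells the reader whether equation (1) is sound, and neither tests whether the effect differs between, say, retired and working caregivers.

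The risk is that an effect is reported as holding in one group and not in another when the two share the same effect and differ only in size or by chance. Interest in such statements is real: the exploratory objectives include describing the dyads that improved most.

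There is also a gap in timing. Burden category is a grouping on the construct that the trial measures as its primary outcome, and receipt of home nursing could change once a coordinator is involved. The SAP does not say at which visit either is taken.

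**Working it through.** **Inputs from the SAP (Sample size estimation).** Difference 7 h/week, SD 20 h/week, 80% power, 5% significance level, 260 dyads before allowance for loss. The Primary efficacy analysis section confirms 2.5% one-sided, equivalent to 5% two-sided.

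**Assumptions.** The SAP gives no subgroup sizes, so splits of 50/50 and 70/30 are used. The trial is approximated by two arms of 130, with precision proportional to the subgroup's share. The true effect is 7 h/week in both subgroups.

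**Reproducing the plan.** n per arm = 2 × (1.96 + 0.842)² × 20² / 7² = 128.1, rounded up to 129, so 258 in total against 260 stated. With 130 per arm, SE = 20 × √(2/130) = 2.48, z = 7/2.48 = 2.82, and power = Φ(2.82 − 1.96) = 81%.

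**Reading A: each subgroup judged by its own significance.** Power in a subgroup with share f is Φ(2.82√f − 1.96). Discordance is p₁(1 − p₂) + p₂(1 − p₁).

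| Split | Power in each subgroup | Exactly one significant |
|---|---|---|
| 50/50 | 51%, 51% | 50% |
| 70/30 | 66%, 34% | 55% |

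With 95% overall power and a 50/50 split, z = 3.605. Each half then has power Φ(3.605 × √0.5 − 1.96) = 72%, and discordance is 2 × 0.72 × 0.28 = 40%. With no effect in either subgroup it is 2 × 0.05 × 0.95 = 9.5%.

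**Reading B: point estimates compared with the overall estimate.** The subgroup-minus-overall difference has SD = SE × √((1 − f)/f). That is 2.48 for a half and 3.79 for a 30% subgroup, whose larger SD governs the 70/30 split.

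| Criterion | 50/50 | 70/30 |
|---|---|---|
| Departs by more than 3.5 h (half the effect) | 16% | 36% |
| Lies outside the overall 95% CI (1.96 × 2.48 = 4.86 h) | 5% | 20% |

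**Reading C: interaction test.** The SE of the between-subgroup difference is SE/√(f(1 − f)), which is 4.96 (50/50) or 5.41 (70/30).
- False difference: 5% per factor by construction. Over seven independent factors, 1 − 0.95⁷ = 30%.
- Power for a between-subgroup difference of 7 h/week: Φ(7/4.96 − 1.96) = 29%, or Φ(7/5.41 − 1.96) = 25%.
- Difference detectable with 80% power: 2.80 × 4.96 = 13.9 h/week, or 2.80 × 5.41 = 15.2 h/week.

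**Timing of the factors.** The SAP calls the subgroup variables covariates, and equation (1) indexes its control variables by time. The Missing data section, in contrast, specifies covariates measured at baseline. RUD and RSS are among the baseline characteristics to be tabulated, so month-0 values exist for grouping on burden, but the Subgroups section does not say that they will be used.

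**The case against.** The strongest reply is that the SAP promises only a comparison. It does not say that subgroups will be declared significant or not, or that claims of difference will follow. Showing subgroup estimates beside the overall one is a common descriptive display, and overlapping data matter mainly when the comparison is treated as a test. No primary or secondary objective rests on the subgroups, and the aim of finding who benefits most is labelled exploratory.

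Much of this stands, and it limits the point. Three stronger readings are tempting and are not supported:
- **That the SAP will contrast subgroup p-values.** The 50% to 55% holds only under that rule, which the text does not state.
- **That this rate applies to seven factors times four primary outcomes (three RUD components and RSS).** The original calculation "aimed to detect a difference of 7 h/week for the primary outcome RUD". The post-hoc calculation concerns PADL only, and no power is given for RSS. The factors are also likely to be related to one another, so 28 separate opportunities cannot be counted.
- **That burden groups will be formed from post-treatment values.** The text leaves this open but does not say so.

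What does not stand is the defence of the rule as a robustness check. A purely descriptive display would be acceptable if labelled as one. The SAP instead places it among the tests meant to support the primary and secondary analyses, and supplies no test of effect modification elsewhere.

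**Conclusion.** The concern holds in this form: the SAP uses subgroup-versus-overall comparison as a robustness check, that comparison cannot serve as one, and nothing in the SAP tests whether effects differ between subgroups.

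The size depends on the unstated reading rule. For the powered RUD outcome with an identical effect in both subgroups, a misleading contrast arises in about 50% to 55% of trials per two-level factor if subgroups are judged by significance. It arises in about 5% to 36% if point estimates are compared. An interaction test would bring it to 5%. These figures rest on the planned effect being true, about 80% overall power, assumed splits and the two-arm approximation. The primary estimate is not affected. What is at risk is the reliability of published subgroup statements.

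**What to change.** Revise the Subgroups section and the robustness section as follows:

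- Move subgroup analyses out of the robustness section and label them exploratory.
- For each factor, fit a treatment-by-factor interaction in the mixed model on all dyads. Use a joint test for factors with more than two levels.
- Include period and factor-by-period terms. Equation (1) writes no period term, although the SAP calls adjustment for time important. Without these terms, different time trends between groups could be read as effect modification.
- Report the effect in each level with its 95% CI, and the interaction estimate with its CI and p-value.
- Define every factor from month-0 values, naming burden category and home nursing explicitly, and state the category boundaries.
- State how the set of tests will be read: about 30% of trials would show at least one false interaction over seven independent factors at 5%. Power is about 25% to 29% for a 7 h/week between-subgroup difference, so a non-significant interaction is not evidence of a uniform effect.

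The cost is SAP wording and a modest amount of extra analysis, with no new data. Fewer subgroup claims will be possible.
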